### **Post-Treatment Follow-Up Period**

During the 12-Month Post-Treatment Follow-Up Period, visits will occur either by phone or on-site from Months 1 through 12.

During the Phone Visits (Post-Treatment Follow-up Visits Month 2, Month 4, Month 5, Month 7, Month 8, Month 10 and Month 11), Site Personnel will discuss adverse events, concomitant medications, if applicable, obtain the results of the subject's self-administered urine pregnancy test and will remind subjects of the importance of consistent use of appropriate and effective dual non-hormonal contraception throughout the Post-Treatment Follow-Up Period. Subjects may begin taking hormonal contraceptive preparations only after completing the Post-Treatment Follow-Up Month 2 Visit and following the return to a full menses (menses with full menstrual flow) in the Post-Treatment Follow-Up Period. If the subject's full menses has not returned by the Post-Treatment Follow-Up Month 2 Visit, an adverse event of amenorrhea should be documented.

Subjects will be required to collect sanitary products for their first menses with full menstrual flow in the Post-Treatment Follow-Up Period. If the subject does not return sanitary products for her first full menses, she will be required to collect and return sanitary products for her next full menses. Subjects will return the sanitary products at a Product Collection Visit within approximately 5 days after cessation of bleeding or spotting. The Post-Treatment UBQ will be administered by Site Staff at each Phone or Site Visit until the subject has returned sanitary products from her first full menses in the Post-Treatment Follow-Up Period. Once a subject returns sanitary products from a full menses in the Post-Treatment Follow-Up Period, the Post-Treatment UBQ no longer needs to be completed.

All subjects will be required to have DXA scans at Post-Treatment Follow-Up Months 6 and 12.

Procedures and assessments in the Post-Treatment Follow-Up Period should be performed as specified in [Appendix C](#), Study Activities.

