**Table 2. Prohibited Medications (Continued)**

Prohibited During the Treatment Period and Post-Treatment Follow-Up Periods	
Bisphosphonates, RANKL inhibitors, Anabolic Bone Agents or rPTH, such as:	Fosamax ® , Fosamax Plus D ® , Binosto ® , Boniva ® , Reclast ® , Zomata ® , Prolia ® , XGEVA, Forteo ® , Actonel ® , Atelvia ® , Miacalcin ® , Fortical ®
Synthetic Prostaglandin E1 (PGE1) Analogs, such as:	Misoprostol (Cytotec ® , Arthrotec ® ) Single use of PGE1 for cervical preparation prior to biopsy is allowed; chronic use is prohibited
Oral Retinoids (topical applications are permitted), such as:	Accutane ® (isotretinoin)

- \* E2/NETA will be taken by subjects randomized to the E2/NETA dose group.
- # Due to the extensive list of herbal remedies and supplements, please contact the AbbVie TA MD for any that may be prohibited.
- % Subjects may begin the use of hormonal contraceptives or tranexamic following completion of the Post-Treatment Follow-Up Month 2 Visit and she has returned to first full menses. Tranexamic acid, if necessary can be prescribed following completion of the Post-Treatment Follow-Up Month 2 Visit and return to first full menses.

If a prohibited medication is necessary to treat an adverse event or a pre-existing condition other than uterine fibroids, the AbbVie TA MD noted in Section 6.1.5 should be consulted; however, if clinically required and to prevent an immediate hazard to the subject being treated, the AbbVie TA MD should be notified as soon as possible after the start of use. Additionally, if a subject takes a prohibited medication during the study, except as permitted per protocol (hormonal medication taken after completion of the Post-Treatment Follow-Up Month 2 Visit and return to first full menses), her continued participation in the study will be evaluated by the Investigator and the AbbVie TA MD. If there are any questions regarding prior or concomitant therapy, please contact your Study Monitor.

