### **5.2.3 Contraception Recommendations and Pregnancy Testing**

#### **Contraception Counseling/Dispense Contraceptives**

Subjects (excluding those subjects who have had a bilateral tubal ligation or bilateral tubal occlusion) will continue to be counseled at every visit throughout their participation in the study on the importance of pregnancy prevention and the use of appropriate and effective

methods of birth control during the Treatment and Post-Treatment Follow-Up Periods of the Extension Study.

Subjects must agree to use two forms of non-hormonal contraception (dual contraception) consistently throughout the Treatment Period and Post-Treatment Follow-Up Periods (Subjects may begin the use of hormonal contraception (e.g., oral or IUD) after completing the Post-Treatment Follow-Up Month 2 Visit and have returned sanitary products for a full menses).

Acceptable methods of dual non-hormonal contraception include the following combinations:

- Condom with spermicide (foam, gel, or polymer film)
- Diaphragm with spermicide (condom may or may not be used)
- Cervical cap with spermicide (condom may or may not be used)

Subjects are not required to use dual contraception methods if:

- Sexual partner(s) is vasectomized at least 6 months prior to Screening
- Subject practices total abstinence from sexual intercourse, as the preferred lifestyle of the subject; periodic abstinence is not acceptable
- Subject had a bilateral tubal occlusion (including ligation and blockage methods such as Essure®) at least 4 months prior to Screening.
- Subject is not sexually active with men; periodic sexual relationship(s) with men requires the use of dual non-hormonal contraception as indicated above.

Subjects may begin the use of hormonal contraception in place of dual non-hormonal contraception during the Post-Treatment Follow-Up Period if they meet both of the following:

- Completed the Post-Treatment Follow-Up Month 2 Visit and
- Returned sanitary products for a full menses in the Post-Treatment Follow-Up Period

If subject does not return to full menses, she must continue use of dual non-hormonal contraception.

The following measures will be taken to help ensure pregnancy prevention during the Extension Study.

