  - Safety labs at Post-Treatment Follow-Up Month 12: Lipid Panel only.
  - A positive urine pregnancy test result must be confirmed with a quantitative serum pregnancy test. For any subject who has a positive serum pregnancy test result, a TVU must be performed during the first trimester of pregnancy to assess the gestational age and estimated date of delivery.
  - Home pregnancy test kit will be self-administered at home by the subject.
  - Subject should return sanitary products within approximately 5 days after cessation of bleeding or spotting from the first menses with full menstrual flow in the Post-Treatment Follow-Up Period at a Product Collection Visit or a scheduled site visit. The venous blood sample will be sent with collected products to the Alkaline Hematin laboratory.
  - Post-Treatment UBQ will only be completed when a Subject has not returned sanitary products for a full menses in the Post-Treatment Follow-Up Period.
  - Subjects are required to continue the use of two forms of non-hormonal birth control. Subjects may begin the use of hormonal contraception in place of non-hormonal birth control after completing the Month 2 Visit in the Post-Treatment Follow-Up Period and the subject has returned products for one full menses.
  - An adverse event of amenorrhea will be reported for subjects who do not return to menses by the Post-Treatment Follow-Up Month 2 Phone Visit and the adverse event will be followed until resolution.

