**If yes, why were sanitary products not collected/returned? (Please select one response)**

- Subject only had spotting that did not require the use of sanitary products\*
- There was no visible blood on sanitary products\*
- Subject forgot to/did not collect\*
- Subject/Site discarded the sanitary products\*
- Subject is still bleeding/spotting; will return when bleeding/spotting complete
- Subject collected sanitary products and did not bring them in yet; will return sanitary products at a later date
- Other

\* Subject will be required to collect sanitary products for her next full menses.

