11.3.5.4 Post-Treatment Menses

The time to first post-treatment menses is defined as the number of days between the last dose date of study drug and the first day of a subject's first post-treatment menses in the Post-Treatment Follow-up Period of the extension study. Menses are defined as having at least 1 day when uterine bleeding categories of bleeding and/or spotting were reported.

Truncated on-treatment menses at the last dose date, i.e., menses that are ongoing at the last dose date will be excluded, and the next occurrence of menses in the Post-Treatment Follow-up Period will be considered as the first post-treatment menses and will be used for reporting the time to first post-treatment menses. If the gap between two consecutive post-treatment menstrual cycles (or between truncated on-treatment menstrual cycle and the next post-treatment menstrual cycle) is 1 day apart or less (i.e., out of the two consecutive cycles, the start date of the second cycle – the end date of the first cycle ≤ 2), these two menstrual cycles will be combined as one menstrual cycle in determining the first post-treatment menses.

AH data will be used for post-treatment menses. If post-treatment menses could not be identified from available AH data, UBQ will be used. For the first UBQ that indicates bleeding ("Subject only has spotting that did not require the use of sanitary products" or "There was no visible blood on the sanitary products" not allowed) after the last dose date, the date of that UBQ will be considered as the first day of the subject's first post-treatment menses.

Volume of bleeding in a subject's first post-treatment menses will be calculated and summarized. Only AH data will be used for volume of bleeding in first post-treatment menses. Time to first post-treatment menses and volume of bleeding in first post-treatment menses will be summarized and analyzed separately for the following groups of subjects:

- All subjects who entered the Post-Treatment Follow-up Period of extension study.
- Subjects who entered the Post-Treatment Follow-up Period and were amenorrhiec at the Final Month in the Treatment Period of extension study. Amenorrhea is defined as in Section 11.3.2.
- Subjects who entered the Post-Treatment Follow-up Period and achieved suppression of bleeding at the Final Month in the Treatment Period of extension study. Suppression of bleeding is defined as in Section 11.3.3.

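### Two different start rules for hormonal contraception in follow-up, and a SAP order that puts AH data before the UBQ, can distort the first post-treatment menses summaries for a probably small number of women

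*Protocol*

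**What the plan says.** **Stricter start rule.** Protocol Section 5.2.3 states it twice, the second time as a list whose items must both be met: Month 2 Visit completed, and "Returned sanitary products for a full menses in the Post-Treatment Follow-Up Period". The follow-up footnotes of Appendix C agree: "after completing the Month 2 Visit in the Post-Treatment Follow-Up Period and the subject has returned products for one full menses".

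**Looser start rule.** The Month 2 Visit plus return to full menses is enough in the synopsis (follow-up paragraph and inclusion criterion 5), Section 5.1, Section 5.2.1 criterion 5, the opening of Section 5.2.2.4, and the numbered pregnancy-prevention measures of Section 5.2.3 itself. The Table 2 footnote has the same rule: "following completion of the Post-Treatment Follow-Up Month 2 Visit and she has returned to first full menses". The paragraph after Table 2 lists "hormonal medication taken after completion of the Post-Treatment Follow-Up Month 2 Visit and return to first full menses" as permitted use, exempt from the review that follows a prohibited medication.

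**Tranexamic acid.** Its start rule is the looser one wherever it appears (synopsis, Section 5.2.2.4, Table 2 footnote).

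**Collection.** Products from the first full menses are due "within approximately 5 days after cessation of bleeding or spotting". If they are not returned, "she will be required to collect and return sanitary products for her next full menses" (Section 5.1). Appendix E repeats this: "Subject will be required to collect sanitary products for her next full menses".

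**Analysis.** SAP 11.3.5.4 identifies the first post-treatment menses from AH data. "If post-treatment menses could not be identified from available AH data, UBQ will be used", and the UBQ's own date then serves as onset. Volume comes from AH data only. One day of bleeding or spotting counts as menses, and menses ongoing at the last dose are excluded. There is no rule for a menses collected on a hormone or on tranexamic acid.

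**The concern.** The two start rules part ways for a woman past Month 2 who has had a full menses but has not returned its products. The protocol expects such women, because it provides a make-up collection for them. The looser wording lets her start a hormone before that make-up menses. It could also be read as letting her start during a first full menses whose products are not yet due. The collected volume would then describe bleeding on a drug rather than return of menses after elagolix. Protocol Section 3.1 itself names oral contraceptives and tranexamic acid as short-term treatments for heavy uterine bleeding.

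The timing question is separate and needs no drug. Time to first post-treatment menses is a listed safety variable (Protocol Sections 5.3.5 and 8.1.8.5). With AH data always taking precedence, a bleed that a site has already recorded on a UBQ is ignored once a later menses is collected.

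**Working it through.** The plan gives no figure to reproduce. The check traces one woman through the rules and then sizes the timing error.

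**Trace (illustrative days after last dose; 28-day cycle assumed)**
1. First full menses begins on day 40. Products are not collected, and she has no earlier post-treatment AH day.
2. The Month 2 Visit falls on nominal day 2 × 28 = 56. The UBQ records the bleeding.
3. Looser rule: she may now start a hormone. Stricter rule: she may not.
4. The make-up menses begins on day 40 + 28 = 68 and is collected.
5. SAP 11.3.5.4: volume is taken from the day-68 menses under either rule. Only the stricter rule keeps it free of a hormone.
6. Time is 68 days (category 57–84) under either rule. True onset was day 40 (category 29–56), and the UBQ date, day 56, is also in 29–56.

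Step 5 depends on which start rule applies. Step 6 does not.

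**Size of the timing error per affected woman**

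Inputs: 28-day categories (SAP 11.3.5.4); cycle lengths of 24, 28 and 35 days (assumptions); onset uniform within a category, days 1–140 (assumption). A delay of D days adds D to the onset day.

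| Delay | Same category | One later | Two later |
|---|---|---|---|
| 24 days | 4/28 = 14% | 24/28 = 86% | 0 |
| 28 days | 0 | 28/28 = 100% | 0 |
| 35 days | 0 | 21/28 = 75% | 7/28 = 25% |

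**How much a UBQ date would recover.** A UBQ date is a contact date. With nominal contacts 28 days apart it falls 0–28 days after onset, mean 14 if onset is uniform between contacts. That is about half of a 28-day delay. With the ±7-day window at both contacts (Protocol Table 1) the gap is 28 ± 14 = 14 to 42 days, so the lag can reach 42 days.

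**How many women.** The documents give no rate of missed collections or of hormone or tranexamic acid starts, so no count is possible. Two facts narrow the group.
- In Phase 2b Cohort 1, among women amenorrheic on entering follow-up, 52% had returned to menses at Month 1 and a further 42% at Month 2: 52 + 42 = 94% (Protocol Section 3.2.2). Few first menses therefore come after the earliest permitted hormone start. The hormone route mainly needs a missed collection as well. This percentage does not limit the timing route, which needs only a missed collection.
- Any earlier collected post-treatment spotting counts as menses under the SAP and takes a woman out of both routes.

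**The case against.** The strongest reply has four parts.

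**The route is narrow and already guarded.** Sites administer the UBQ at each contact until products come back, non-collectors must collect the next full menses, and medication dates are recorded. A site that follows the explicit two-part test in Section 5.2.3 also satisfies every looser statement. This stands as to size. It does not remove the conflict, because the text after Table 2 tells sites that use under the looser rule is permitted.

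**The day counts do not measure the hormone problem.** Correct. They size the AH-before-UBQ order only. No volume bias can be estimated from the documents.

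**The obvious repairs can do harm.** A reader might infer that menses collected on a hormone or tranexamic acid should simply be dropped. Because tranexamic acid is taken for heavy bleeding, dropping those menses would tend to remove the heaviest bleeds and lower the summarised volume. A reader might also infer that any earlier UBQ should override the AH date. The UBQ asks only about bleeding since the last visit and gives no onset date, so an uncollected on-treatment bleed could displace a true AH onset. Both objections stand and shape the fix.

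**Extending the stricter rule keeps some women longer on barrier methods for the sake of a descriptive variable.** True, and it belongs among the costs. Section 5.2.3 and Appendix C already require it, however.

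**Conclusion.** Both defects are real and minor. The wording conflict is plain on the page, and under the looser wording a menses collected on a hormone can supply the first post-treatment volume. The AH-before-UBQ order gives a date about one cycle late for a woman whose uncollected first menses was already reported on a UBQ and who has no earlier post-treatment AH day. That is one 28-day category if her cycle is 28 days.

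The number of women is unknown and probably small. That judgement rests on Phase 2b return-to-menses figures for women amenorrheic at follow-up entry, and on the repeated UBQ contacts, not on any observed collection rate.

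Three stronger readings are not supported:
- *The efficacy conclusions are affected.* The primary endpoint uses the last 28 days of treatment, and SAP 12.1 plans no testing of post-treatment safety endpoints. Only descriptive summaries change.
- *Starting a hormone under the looser rule is a deviation.* The protocol calls it permitted.
- *The tranexamic acid rule is also inconsistent.* It reads the same throughout. The gap there is only that the SAP does not say how to treat a menses collected on the drug.

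**What to change.** 1. **Protocol.** Wherever the hormonal contraception start rule appears, use the condition in Section 5.2.3 and Appendix C: Month 2 Visit completed and products returned for a full menses. Leave the tranexamic acid rule unchanged, which means separating the two drugs where the synopsis and the Table 2 footnote treat them together.
2. **SAP 11.3.5.4, volume.** Flag any first post-treatment menses before or during which hormonal contraception or tranexamic acid was started, using the medication dates recorded under Protocol Section 5.2.2.1 and already summarised under SAP 8.3. Keep all women in the main summary and repeat it without the flagged menses, noting that removing tranexamic acid users may remove the heaviest bleeds.
3. **SAP 11.3.5.4, time.** For all women, take the earlier of the first AH-identified menses and the first UBQ reporting bleeding, as the SAP defines it, whose products were never returned. Accept the UBQ only if its reporting interval starts on or after the last dose and the bleeding was not ongoing at last dose. State that a UBQ date is an upper bound on true onset.

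**Cost.** Item 1 is a wording amendment that touches an inclusion criterion and needs IEC/IRB approval (Protocol Section 9.1). Women who missed the collection stay on dual barrier contraception for about one more cycle, with the pregnancy risk that carries; the programme had 46 post-treatment pregnancies at the February 2016 count (Protocol Section 3.2.2.1). Items 2 and 3 are two added SAP rules and need no new data. If an amendment is not worthwhile, items 2 and 3 alone would protect the summaries.

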### **Pregnancy Tests and Reporting a Pregnancy**

Urine and/or serum pregnancy tests will be performed as specified in [Appendix C](#), Study Activities, in all subjects regardless of sexual activity status or method of contraception.

The subject must have a confirmed negative urine pregnancy test within 24 hours prior to performing endometrial biopsy or SIS (if applicable).

The urine and serum pregnancy tests performed at the Final Treatment Visit (Month 6 or Unscheduled Visit just prior to roll-over into the Extension Study) of the Pivotal Study will serve to assess subject eligibility for entry into this Extension Study and the urine pregnancy test result must be reviewed and determined to be negative prior to registering the subject in IRT. If the Final Treatment Visit in the Pivotal Study (just prior to roll-over into this Extension Study) does not occur on the same day as Day 1 of this Extension Study, a urine pregnancy test must be performed at Day 1 and a negative urine pregnancy test result must be obtained prior to administration of the first dose of study drug in this Extension Study.

Urine pregnancy test results must be negative prior to providing subjects with their Day 1 and subsequent supply of study drug, (including an Unscheduled Visit at which study drug is dispensed).

Home pregnancy test kits will be provided to the subject at the Day 1 Visit and Month 6 or Premature Discontinuation Visit during the Treatment Period when logistically, a urine pregnancy test cannot be performed at the study site or other medical facility within 24 hours prior to an endometrial biopsy or SIS (if applicable). The subject must self-administer and report a negative urine pregnancy test result to the site within 24 hours prior to undergoing these procedures.

A positive urine pregnancy test result must be confirmed with a quantitative serum pregnancy test. The subject should temporarily discontinue study drug administration while waiting for the results of the serum pregnancy test. If a serum pregnancy test result is positive at any time during the Treatment Period, the site will immediately inform the subject to discontinue study drug (Section 6.1.6). If a subject is confirmed as pregnant, the subject will be prematurely discontinued from the study.

An ultrasound examination will be performed during the first trimester of pregnancy to assess the gestational age and estimated date of delivery if the subject becomes pregnant during the Treatment or Post-Treatment Follow-Up Periods of the study. Refer to Section 6.1.6 for instructions on reporting of a pregnancy to the Sponsor and the required follow-up on the subject/fetus and live infant births.

### **5.3 Efficacy, Pharmacokinetic, Pharmacodynamic, Pharmacogenetic and Safety Assessments/Variables**

#### **5.3.1 Efficacy and Safety Measurements Assessed and Flow Chart**

Study procedures during the Treatment and Post-Treatment Follow-Up Periods described in this protocol are summarized in [Appendix C](#), Study Activities.

##### **5.3.1.1 Study Procedures**

Subjects entering into this Extension Study will have completed all Month 6 study procedures in their respective pivotal study, Studies M12-815 or M12-817, and following availability of all assessment results, the subject will have been determined to be eligible for this Extension Study.

Study procedures in this Extension Study begin on Day 1 and should be conducted as per [Appendix C](#), Study Activities. When the Day 1 Visit occurs on the same day as the Final Treatment Visit of the respective Pivotal Study, assessments and procedures performed at the Final Treatment Visit should not be repeated at the Day 1 Visit of this Extension Study, unless deemed necessary by the Principal Investigator.

The study procedures outlined in [Appendix C](#), Study Activities, are discussed in detail in this section, with the exception of the monitoring of study drug accountability (Section 5.5.7) and the collection of concomitant medication and adverse event information (Section 5.2.2.1 and Section 6.1, respectively). Study data will be recorded on eCRFs with the exception of several PRO questionnaires that will be recorded on source documents and on eCRFs.

Study procedures during the Treatment and Post-Treatment Follow-Up Periods may be performed within the visit windows specified in [Table 1](#). Scheduled monthly visits during the Treatment and Post-Treatment Follow-Up Period are based on a 28-day month.

This protocol provides recommendations regarding the sequence of procedures to be performed during the study. In no case should these recommendations outweigh clinical judgment or standard of care. If the protocol indicates that the AbbVie TA MD is to be contacted prior to performing a procedure, yet the timing of the request would either interrupt a procedure or would interfere with standard of care and clinical judgment, then clinical judgment should prevail and the AbbVie TA MD should be notified afterwards.

When findings of past medical, surgical, gynecological or uterine fibroid history are identified, the relevant eCRF(s) and Source Note(s) of the Pivotal Study (Studies M12-815 or M12-817) should be updated, unless otherwise instructed by the Monitor.

